6. SELECTION & RECRUITMENT OF PARTICIPANTS

Study Participants

Study participants will include up to 600 caregivers of youth with epilepsy between 2-12 years old at CCHMC and collaborating sites. Caregivers will be recruited during routine medical appointments with neurology or epilepsy-related hospital visits and will meet the following inclusion/exclusion criteria:

Inclusion criteria

- Child age 2-12 years old
- Diagnosis of epilepsy within the last 2 years
- On ≤ 2 antiepileptic drugs (AEDs)
- Ability to read and speak English

Exclusion criteria

- Diagnosis of non-epilepsy medical disorders requiring daily medications (Asthma, allergies, ADHD, and daily vitamins are okay)
- Diagnosis of severe behavioral disruption, developmental delays (global), and Autism Spectrum Disorder (DSM 5 Level 2 or 3 severity) based on medical chart review and/or parent report. "Severe" is defined as children who:
 - 1) have an IQ < 70 if documented
 - 2) are nonverbal
 - 3) have impaired thinking
 - 4) have aggressive behaviors
 - 5) have "global developmental delay"
 - 6) use a school aide (i.e. someone providing 1:1 help in the classroom)

Recruitment Procedures

Potential participants meeting eligibility criteria will be identified by a trained research coordinator in collaboration with the epilepsy team. If potential participants are eligible, a trained research coordinator will approach families during their medical clinic visit. A thorough overview of the study will be provided, including study procedures, benefits, and risks. *Research coordinators will verify all inclusion/exclusion criteria as noted above.* A study figure will also be given to families to understand the design and timeline of the trial (See Appendix A). All questions will be addressed and informed consent/assent will be obtained (see Section 7).

Following informed consent from the caregiver/legal guardian and child assent (11 years and older), electronic pillbox and pill bottles will be provided, and baseline questionnaires will be completed via REDCap. The recruitment script can be found in Appendix B and other recruitment materials can also be found in the appendices, including flyers, study magnets (Appendix C). Recruitment materials will be used in various places to help recruit participants (e.g. flyers posted on hospital specific social media sites, distributed in clinic, etc.). Notably, this trial is focused on serving at least 30% of those that are underrepresented.

Underrepresentation is defined as minority race/ethnicity, public/no insurance status, and living in a region that is rural or medically underserved based on HRSA maps. We will track the number of participants that meet these criteria throughout the trial to ensure at least 30% of our participants are underrepresented. The medical chart review will provide data on this status.

7. PROCESS OF OBTAINING CONSENT

As noted above, once participants are identified as study eligible, they will be approached during their epilepsy clinic visit and provided a description of the study (e.g., study procedures, benefits, risks) by a trained research coordinator included on the approved IRB protocol. After addressing all questions from potential participants, informed consent/assent will be obtained by trained research staff. Consent forms will be signed electronically using REDCap, a secure web- based interface supported by the CCHMC Division of Biomedical Informatics in compliance with HIPAA designed to protect PHI in the electronic transfer and storage of the consent form.

Should technical issues arise with the REDCap interface, hard copies of consent forms may also be used. For all consent visits, all pertinent aspects of consent will be covered including study purpose, risks/benefits, confidentiality, and right to withdraw. Patients will be informed that their care at CCHMC or other collaborating study sites will not be affected by whether they choose to participate in the study.

If the caregiver agrees to participate and is signing an electronic consent form via REDCap, they will have an opportunity to check a box stating that they agree to provide their consent. There will also be fields for their typed name, date, and electronic signature to document the informed consent process. Once the electronic form has been submitted, caregivers will receive a copy of the electronically signed and dated consent form via email.

[figure not shown]
Participants recruited in-person will complete the informed consent document in-person. For participants who decide to participate after the clinic visit, we will use telephonic electronic consent. Specifically, a member of the study team will provide a link to access the consent form in REDCap via email or text message. A hard copy of the consent form may also be mailed if necessary. During the consent/assent phone call, research staff will ensure all questions are answered. In compliance with CCHMC SOP Number 41-1.6, study staff will sign and date accordingly on the signature page of each form corresponding to the date the forms were received, not necessarily reviewed with the family. The method used to obtain participant consent will also be written on the Informed Consent Process Note.

8. STUDY PROCEDURES

This is a longitudinal study of caregivers of children with epilepsy that will employ SMART methodology to test the efficacy and effectiveness of a mHealth adherence intervention. Potential participants will be identified by the study coordinator in collaboration with the epilepsy team at each site as noted above. After caregivers provide informed consent (see Section 7), baseline questionnaires will be completed via REDCap, including a demographics form and study measure questionnaires (see Measures section below). All measures will be hosted on REDCap, a secure web-based interface. The PI and her team have fully tested REDCap questionnaires and will test prior to study implementation across all sites to ensure functionality. A medical chart review will also be conducted to gather information about seizures, medications,

seizure etiology, comorbidities, and time since diagnosis. It is notable that the participant must provide an email address for the online questionnaires. If they do not have one, we will help them create one or we will text the link to their cellular phones, if needed.

The eACT SMART design is illustrated in Figure 1 below. All participant families will complete a 2-month baseline period during which they will use electronic adherence monitoring (i.e., pillbox or pill bottle) to measure adherence. Participants who demonstrate adherence $\leq 95\%$ will move on to Stage 1 SMART for randomization. In SMART Stage 1 (3-months), caregivers will be randomized to control group (mHealth education microlearning sessions and module and automated digital reminders) or treatment (control condition plus individualized adherence feedback reports)

- **Education microlearning sessions:** The 4-5 education microlearning sessions will take approximately 5-10 minutes to complete on any mobile device, tablet or computer. All caregivers will be provided with a link to the portal with their log-in information following the baseline period to obtain access to the microlearning sessions. These sessions have information regarding the diagnosis of epilepsy, treatment, rationale for adherence, and other epilepsy facts that caregivers have found beneficial.
- **Automated Digital Reminders** – Each adherence electronic monitor has the capability to provide automated digital reminders. As a part of the intervention, all caregivers randomized to intervention will have the option of selecting the type of automated digital reminders that they receive, which could include text messages and/or device sounds/lights. These will be turned on immediately following the baseline period based on the participant's preferences.
- **Individualized Adherence Feedback Reports** - Individualized adherence feedback will be received by families once a week where they will be provided with information about

adherence levels over the previous 7 days based on their electronic adherence monitors. All individualized adherence feedback reports will be received on Monday. A separate portal has been developed by Bioinformatics at CCHMC to create the adherence feedback reports. Data from the SimpleMed pillbox via open API and AdhereTech via excel spreadsheets are merged to provide a calendar plot with the participant's adherence data from the past week. The participant will receive a push notification to view their adherence from the past week. The portal with this information will use the same log-in information as the education and problem-solving sessions. It is notable that the participant must provide a cell phone number for the push notifications.

At the beginning of SMART Stage 2 (2-months), caregivers randomized to the treatment group who demonstrate continued non-adherence (<95%; non-response) by the end of Stage 1 will undergo a second randomization to either 1) continued individualized adherence feedback or 2) individualized adherence feedback augmented with a mHealth problem-solving module and two therapist-guided sessions using Zoom for healthcare. The mHealth problem-solving module incorporates a video and reviews skills of problem-solving for caregivers of young children with epilepsy and takes approximately 10 minutes to view from any mobile device, tablet or computer. The same log-in information for the education microlearning sessions will be used to access the problem solving modules. Following completion of the problem-solving module, a therapist will contact the family to review and apply the problem-solving skills. Two sessions will occur one month apart via teleconferencing (i.e., Zoom for Healthcare-Appendix D), which is a HIPAA-compliant teleconferencing site.

After completion of Stage 2, automated digital reminders will be turned off and adherence feedback reports will cease to be provided. Additional questionnaires will be completed via REDCap at Post-Treatment (1-Month Follow-Up in Month 8), Follow-Up 1 (6 months post-treatment in Month 14)*, and Follow-Up 2 (12 months post-treatment in Month 20)**.

Data collection procedures and measures: Participants will complete a demographic questionnaire that provides general information about the child's age, caregiver work history, family composition, socio-economic status, family history of seizures, history of seizures (e.g., type, who witness, when they occurred), and comorbid illnesses (e.g., learning disorders). In addition, caregivers will complete the questionnaires detailed in the table below.

Construct Measured	Respondent C=Caregiver; M=Medical Chart Review D=Doctor/Clinician	Stages and Time points			
		Baseline	Post (1 month post- treatment)	Follow-Up 1 (6 months post- treatment) *	Follow-Up 2 (12 months post- treatment) **
ORDER OF MEASURES (As applicable)					
Background Form (Demographic)	C	X			
Pediatric Epilepsy Medication Self-Management Questionnaire (PEMSQ) 
 PEMSQ: Self-reported Adherence 	C	X	X	X	X
Behavior Assessment System for Children-3 Parent-Rating Scales	C	X	X	X	X
Short Test of Functional Health Literacy in Adults	C	X	X	X	X
Pediatric Quality of Life in Epilepsy Module	C	X	X	X	X
Brief Symptom Inventory-18 (BSI-18)	C	X	X	X	X
Epilepsy Knowledge Questionnaire-Adapted (EKQ)	C	X	X	X	X

Social Problem-Solving Inventory-Revised Short (SPSI-Revised Short)	C	X	X	X	X
Pediatric Epilepsy Side Effects Questionnaire (PESQ)	C	X	X	X	X
Seizure Severity Scale Adapted for Children (SSSC)	C	X	X	X	X
Family Assessment Device (FAD)	C	X	X	X	X
Global Assessment of the Severity Scale of Epilepsy in Children (GASE)	D	X	X	X	X
Healthcare utilization	C	X	X	X	X
Medical Chart Review	M	X	X	X	X
Feasibility/Acceptability Questionnaire (FAQ)	C		X		
Impact of COVID-19 on Pediatric Epilepsy Management (ICPEM)	C	X	X	X	X

*Follow-Up 1 Questionnaires will only be completed by participants enrolled before 3/8/2023

**Follow-Up 2 Questionnaires will only be completed by participants enrolled before 12/9/2022

An additional questionnaire related to the child's seizure severity (one item) will be obtained from the child's epilepsy provider. A medical chart review will also be conducted to describe key patient medical characteristics (e.g., epilepsy type and treatment, seizure frequency, quality of life, side effects, hospitalizations, emergency room visits, and telephone contacts to clinic staff between routine clinic visits). Chart reviews will cover the entire study period. *Due to the unexpected COVID-19 pandemic, we are also including a newly-developed measure, the Impact of COVID-19 on Pediatric Epilepsy Management (ICPEM) to understand how COVID-19 is impacting our research participants and the outcomes of our study.*

Raw adherence data will be obtained from the SimpleMed pillbox and AdhereTech bottles and will be used as the primary outcome variable. Data from these devices is obtained real-time via blue-tooth and 4G technology and thus will require no additional burden for participants. They will simply put their anti-seizure medicine in the electronic monitor (those who already use bottles will be given an AdhereTech bottle and those who use pillboxes will be given SimpleMed pillboxes).

To increase retention, we will be sending thank you letters, birthday cards and holiday cards (See Appendix E). We will also be providing all participants with a study folder with materials that may be helpful during the study, such as an introductory letter, study timeline, information about their electronic monitor, and our contact information (See Appendix F).

8.1 Sample Size Considerations and Power Analysis: Power analysis was conducted based on SMART Stage 1, assuming ~180 participants randomized to treatment and ~90 to control group. Effect sizes for education-focused adherence interventions with reminders in other chronic conditions relative to controls (e.g., treatment as usual, pre-post) range from 0.08-0.20,^{72,170} while those with adherence feedback range from 0.78-1.03.^{80,171} Power for the primary analysis (Aim 1 below) will be 80% to detect a small-to-moderate standardized effect size (Cohen's $d=0.36$) and 97% to detect a moderate standardized effect size (Cohen's $d=0.50$). These detectable effect sizes reflect clinically meaningful changes in adherence. Power analyses require known and unknown assumptions, such as the anticipated response rate to Education + Automated Digital Reminders + Individualized Adherence Feedback at the end of Stage 1. Effect sizes for our face-to-face problem-solving adherence intervention, which incorporates IAF relative to treatment as usual, ranged from 0.95 (1st problem-solving session) to 1.59 (2nd problem-solving session).¹⁵ Assuming a 50% response rate to SMART Stage 1 treatment and a Bonferroni multiplicity adjustment, the proposed sample size provides 80% power with alpha at 0.05 to detect a standardized effect size of $d=0.69$ between any pair of embedded strategies (SMART Stage 2).

8.2. Data Analysis: All data analysis and management will also occur at North Carolina State University (NC State), which is the primary data analysis site. The Division of Behavioral Medicine and Clinical Psychology at CCHMC has developed a Divisional Data Core (DDC) in cooperation with the divisions of Biostatistics and Epidemiology and Bioinformatics to share the de-identified data with NC State. The CCHMC DDC will provide quality reports to audit the data routinely, provide data for safety monitoring committee reports for the biostatisticians at NC State, and cleaning of the data.

Aim 1: Examine the efficacy of the mHealth adherence intervention in caregivers of children (ages 2-12) with newly diagnosed epilepsy (< 2 years) on electronically monitored adherence. Electronically-monitored adherence, measured on a scale of 0-100%, will be calculated for the final 30 days of Stage 1 SMART. The primary outcome is percent change in adherence from baseline, calculated using the baseline and final 30-day adherence. The primary hypothesis is that participants initially randomized to treatment (E+ADR+IAF) will exhibit significantly greater improvements in adherence compared to those randomized to control (E+ADR) from baseline to end of Stage 1 (i.e., last 30 days). A two-sided, two-sample t-test with unequal sample sizes will be used for the primary analysis. *Exploratory Analyses:* Daily electronically-monitored adherence will be available on each participant throughout the SMART. To gain insight into the possible differences in the evolution of adherence following introduction of each intervention strategy, we will use functional data analysis methods¹⁷² to evaluate and contrast patterns of longitudinal adherence. Functional principal components will be used to estimate a small set of representative adherence patterns associated with each treatment; these patterns will improve understanding of patient trajectories and inform future interventions (e.g., identifying when ADR might be most effective).

Aim 2: To compare the effectiveness of the three intervention strategies on adherence, seizure severity/frequency, quality of life, and healthcare utilization at 1-, 6-, and 12-months post-intervention. We will carry out secondary analyses to compare the three intervention strategies embedded in the SMART: #1 E+ADR (control), continuing regardless of response at three months; #2 E+ADR+IAF (treatment), continuing regardless of response; and #3 E+ADR+IAF+Problem-solving if not responsive. Strategies #1 and #2 are non-adaptive intervention strategies in that treatment is not modified in accordance with response status (or any other participant characteristics); #3 is an adaptive intervention strategy in that treatment is augmented by problem-solving only among non-responders. The pairwise comparison of the non-adaptive strategy #1 to the adaptive strategy #3 represents comparison of the least resource-intensive, least burdensome strategy to the most resource-intensive, most burdensome strategy. Note that the actual experience of a participant may be consistent with more than one embedded strategy; in particular, a participant who receives E+ADR+IAF initially, responds, and continues to receive E+ADR+IAF is consistent with having followed either strategy #2 or #3. Thus, such a participant's data contribute to assessment of improvement in adherence for both of these strategies. Comparison of strategies #1, #2, and #3 requires the use of specialized methods¹³³ that account for the fact that actual experiences of participants may be consistent with more than one strategy. We will conduct pairwise comparisons of the three embedded strategies on the basis of adherence, seizure severity/frequency, quality of life, and healthcare utilization at 1-, 6-, and 12-months post-intervention. Appropriate methods will be used based on the type of outcome measure: binary, count, and continuous variables.

Aim 3: To identify individual and family characteristics that predict responsiveness to the three intervention strategies and to derive an optimal, adaptive intervention strategy for tailoring selection of initial and subsequent intervention in the case of nonresponse based on individual characteristics. The data collected in the SMART will provide a rich resource for investigating participant baseline characteristics and post-randomization characteristics ascertained prior to response status that can inform tailored selection of initial (E+ADR+IAF or control) and subsequent adherence strategies (continue E+ADR+IAF or augment with problem-solving) for children who do not initially respond to E+ADR+IAF. We will

carry out several exploratory, hypothesis-generating analyses. We will use standard methods based on linear models for percent improvement in adherence to evaluate baseline characteristics that are moderators of participants' adherence status following initial intervention. We will also use standard tests for qualitative interactions¹⁷³ and more recent variable selection methods for qualitative interactions that adjust for multiplicity.^{174,175} Evaluation of moderators of outcomes at 1-, 6-, and 12-months post-intervention is complicated by the sequential nature of the interventions, requiring the use of specialized statistical methods. We will use Q-learning¹⁷⁶ and value-search estimation^{129,130} to test for moderators of the initial and stepped up interventions. We will first conduct an overall test of the null hypothesis that there are no moderators at either stage. If the test rejects this null hypothesis, we will conduct appropriate multiplicity-adjusted statistical tests to identify specific baseline and intermediate moderators of outcomes at 1-, 6-, and 12-month follow-ups. Because of the sequential nature of the interventions, standard statistical tests are invalid without appropriate modification.^{132,177} We will use suitable bootstrap methods to ensure that the tests are valid (i.e., have correct control for Type 1 error). We will also use Q-learning and value-search estimation^{111,112} to estimate an optimal adaptive intervention strategy for personalizing selection of initial intervention and the need for stepped up care following E+ADR+IAF based on child/caregiver characteristics. We will evaluate the potential improvement in adherence that could have been realized for each participant in the SMART if s/he had received initial and secondary interventions via the optimal adaptive intervention strategy. We will also carry out Monte Carlo simulations to compare the average percent improvement in adherence achievable using the optimal adaptive intervention strategy to those achievable using the simpler embedded strategies #1- #3. This analysis will provide valuable insight on key characteristics implicated in heterogeneous intervention effects and subgroups and form the basis for formulation of personalized intervention strategies for subsequent study.

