**Epilepsy Adherence in Children and Technology (eACT): Fostering
Medication Adherence in Children With Epilepsy Using mHealth
Technology**

Clinicaltrials.gov NCT03817229

Unique Protocol ID: 2018-8411

Version 1.0-5/20/25

Power and Sample Size Estimation

Sample size estimation was informed by results of previous studies of adherence interventions. Effect sizes for education-focused adherence interventions with reminders in other chronic conditions relative to controls (e.g., treatment as usual, pre-post) range from 0.08-0.20 [42, 43], while those with adherence feedback range from 0.78-1.03 [44, 45]. Specifically, an HIV study found that individualized adherence feedback demonstrated a large, standardized effect size (Cohen's $d=0.78$) [44]. Similar and higher effect sizes have been found for mHealth interventions that include education, automated digital reminders, or individualized feedback in adult samples including asthma, diabetes, and heart disease (Cohen's $d=0.70-2.51$) [46-48].

Given the range of observed effect sizes and taking into account the size of clinically meaningful changes in adherence, sample size was determined to detect a small-to-moderate standardized effect size (Cohen's $d=0.36$) for the primary analysis of SMART Stage 1 comparing intervention to control with 80% power with significance level 0.05. Assuming 2:1 randomization to intervention vs control yields a conservative total sample size estimate of 270, with ~180 participants randomized to intervention and ~90 to control. This sample size leads to 97% power to detect a moderate standardized effect size (Cohen's $d=0.50$).

Power for the secondary analysis involving pairwise comparison of the intervention strategies embedded in the SMART is informed by effect sizes for our face-to-face problem-solving adherence intervention, which incorporates individualized adherence feedback relative to treatment as usual. These effect sizes ranged from from 0.95 (1st problem-solving session) to 1.59 (2nd problem-solving session). Power analyses for comparison of intervention strategies require additional unknown assumptions, such as the anticipated response rate to intervention at the end of Stage 1. Assuming a 50% response rate to SMART Stage 1 intervention and a Bonferroni multiplicity adjustment, the proposed sample size provides 80% power with significance level 0.05 to detect a standardized effect size of $d=0.69$ between any pair of the embedded intervention strategies #1 - #3.

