To achieve the proposed sample size, the planned study sample was 600 participants across sites, with the goal of approximately 330 of the 600 being randomized (i.e., 10% attrition during the baseline phase, and 45% would be > 95% adherent, completing the study before randomization) [5]. Following initial randomization, these ~300 participants were to be assigned in a 2:1 ratio to intervention ($n=200$) and control ($n=100$). Making a conservative assumption of 10% attrition of participants in each initial SMART intervention arm results in anticipated $n=180$ randomized to intervention and $n=90$ randomized to control at the end of Stage 1. However, per federal and institution specific guidelines, recruitment was suspended during the COVID-19 pandemic, and the study team determined that 450 participants would need to be enrolled for $n=180$ to be randomized to the intervention arm and $n=90$ randomized to the control arm.

Statistical Analysis Plan

Primary Analysis Plan:

An intent to treat approach will be undertaken for all analyses, and a significance level of 0.05 will be used. The primary analysis examines the efficacy of the mHealth adherence intervention in caregivers of youth (ages 2-12) with newly diagnosed epilepsy (< 2 years) on electronically monitored adherence relative to control on the basis of the primary outcome of change in electronically monitored adherence from baseline, calculated using the baseline and final 30-day adherence. The primary hypothesis is that participants initially randomized to intervention will exhibit significantly greater improvements in adherence compared to those randomized to control from baseline to end of Stage 1. Although sample size was calculated conservatively based on use of a two-sided, two-sample t -test with unequal sample sizes, to achieve a more efficient analysis with enhanced power, the primary analysis will be based on a standard analysis of covariance with adherence at the end of Stage 1 as the dependent variable and baseline adherence as the covariate.

Secondary Analysis Plan:

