The data collected will provide a rich resource for exploratory analyses investigating participant baseline characteristics and post-randomization characteristics ascertained prior to assessment of Stage 1 adherence status that can inform tailored selection of initial intervention (intervention or control) and of subsequent intervention for non-adherent individuals receiving initial intervention (continue intervention or augment intervention with problem solving). We will use standard methods to evaluate whether baseline characteristics moderate participants' adherence status following initial intervention, including tests for qualitative interactions. Evaluation of moderators of outcomes at Stage 2 and at 1-, 6-, and 12-months post-intervention is complicated by the sequential nature of the interventions, requiring the use of specialized statistical methods, such as Q-learning and value-search estimation. We will also use these methods to estimate an optimal adaptive intervention strategy for individualizing selection of initial intervention and intervention in the case of non-adherence based on baseline and evolving child/family characteristics, informing strategies for future study.

Handling of Missing Data:

Missing change in adherence outcomes in the primary analysis will be addressed in several ways. Under the assumption that the adherence outcomes are exactly normally distributed and linearly related, the analysis of covariance based on the complete cases will yield valid inferences under the assumption of missing at random (MAR). To evaluate the evidence in the data under MAR without making the restrictive assumptions of normality and linearity, we will conduct the complete case analysis if missingness is nondifferential by Stage 1 assignment and less than 10% in each assignment group. To assess sensitivity of this analysis to missingness, under the assumption of MAR, we will also conduct an inverse probability weighted complete case analysis of covariance in which outcomes are weighted by the reciprocal of the estimated probability not dropping out of the study in Stage 1 based on a

logistic regression model that incorporates baseline variables associated with failure to complete Stage 1.

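### Exploratory Aim 3 values the estimated optimal strategy on the same participants used to derive it, with no optimism correction, so its reported gain is biased upward

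*Protocol*

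**What the plan says.** Protocol Section 8.2, Aim 3, applies Q-learning and value-search estimation to the trial's own data to obtain an optimal adaptive strategy. The valuation follows directly: "We will evaluate the potential improvement in adherence that could have been realized for each participant in the SMART if s/he had received" what that strategy would have chosen. A separate sentence plans Monte Carlo work with this purpose: "compare the average percent improvement in adherence achievable using the optimal adaptive intervention strategy to those achievable using the simpler embedded strategies" (those numbered #1 to #3). It does not say what model generates the simulated data.

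The same section contains three safeguards, all aimed at finding moderators. They are an overall test that no moderator exists at either stage, multiplicity-adjusted variable selection for qualitative interactions, and a bootstrap to control Type 1 error in the tests. None is stated to apply to the value of the derived strategy. The section labels the work exploratory and closes by presenting it as groundwork for personalised strategies to be studied later.

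The SAP's Exploratory Analysis Plan keeps the intention to "estimate an optimal adaptive intervention strategy for individualizing selection of initial intervention" and later intervention. It contains neither the per-participant valuation nor the comparison with #1 to #3. Neither document mentions sample splitting, cross-validation or an optimism correction for the strategy's value.

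**The concern.** A rule chosen to maximise fitted adherence in a set of participants fits their noise as well as any real heterogeneity. Scoring it on those participants counts the noise as benefit. Strategies #1 to #3 are fixed by design, so none of them is fitted to the data in this way. A personalised strategy can therefore look better than all three when tailoring adds nothing, and even when the derived rule is worse than simply using one of them.

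What is at stake is the judgement on whether a personalised strategy deserves a follow-on trial.

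**Working it through.** **Inputs from the documents.** Stage 1 sizes: "assuming ~180 participants randomized to treatment and ~90 to control group" (Protocol 8.1). Allocation: "Assuming 2:1 randomization to intervention vs control yields a conservative total sample size estimate of 270" (SAP, Power and Sample Size Estimation). Level: "a significance level of 0.05 will be used" (SAP, Primary Analysis Plan). Test behind the power figure: "A two-sided, two-sample t-test with unequal sample sizes will be used for the primary analysis" (Protocol 8.2, Aim 1). Response rate 50%, with Bonferroni adjustment over three pairs (Protocol 8.1).

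**Assumptions not in the documents.** Second randomization 1:1; K independent normal baseline covariates, with K = 1, 3, 5 or 10; linear Q-functions; normal outcome with SD 1. Value-search estimation was not simulated.

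**Step 1: reproduce the plan's figures.** The documents give no figure for the Aim 3 comparison, so the check is on the stated power.
- d = 0.36: 0.36 × √(90×180/270) = 0.36 × √60 = 2.79; Φ(2.79 − 1.96) = 79.6% (79.3% by noncentral t), against 80% stated.
- d = 0.50: 0.50 × √60 = 3.87; Φ(3.87 − 1.96) = 97.2% (97.1%), against 97%.
- d = 0.69 with 45 versus 45 re-randomized non-responders at 0.05/3: 0.69 × √22.5 = 3.27; Φ(3.27 − 2.39) = 81.0% (79.5%), against 80%.

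All agree, so the design simulated is the one the plan describes.

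**Step 2: simulate with no true moderator.** Each setting has 600 simulated trials (90 control, 180 treatment), analysed by two-stage linear Q-learning. With the 0.69 effect in non-responders, the true value of #3 is 0.36 + 0.5 × 0.69 = 0.705. Values are in SD units. The last two columns compare the same-sample value with the largest of the three embedded estimates in the same trial.

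| True effects | K | Same-sample value | True value of derived rule | 10-fold cross-validated | True best embedded | Mean excess | Trials with excess |
|---|---|---|---|---|---|---|---|
| None | 3 | 0.149 | 0.000 | 0.003 | 0.000 | 0.073 | 98% |
| None | 5 | 0.191 | 0.000 | 0.011 | 0.000 | 0.115 | 99.7% |
| None | 10 | 0.268 | 0.000 | 0.006 | 0.000 | 0.187 | 100% |
| Stage 1 0.36 | 3 | 0.453 | 0.344 | 0.342 | 0.360 | 0.048 | 97% |
| Stage 1 0.36 | 5 | 0.476 | 0.333 | 0.323 | 0.360 | 0.073 | 99% |
| Stage 1 0.36 | 10 | 0.543 | 0.314 | 0.319 | 0.360 | 0.137 | 100% |
| 0.36 and 0.69 | 3 | 0.717 | 0.679 | 0.678 | 0.705 | 0.010 | 69% |
| 0.36 and 0.69 | 5 | 0.716 | 0.655 | 0.645 | 0.705 | 0.017 | 73% |
| 0.36 and 0.69 | 10 | 0.761 | 0.608 | 0.599 | 0.705 | 0.050 | 89% |

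With one covariate the excess is 0.027, 0.016 and 0.002 SD in the three scenarios. A separate simulation of the no-effects case gave an excess of about 0.08 to 0.18 SD for K = 3 to 10, within 0.01 of the table.

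Three readings follow.
- The optimism in the value itself (same-sample minus true) is 0.149 to 0.268 with no effects. It is 0.453 − 0.344 = 0.109 to 0.543 − 0.314 = 0.229 with the Stage 1 effect, and 0.717 − 0.679 = 0.038 to 0.761 − 0.608 = 0.153 with both effects. It persists even where the excess over #3 is small.
- Inverse probability weighting in the same sample does not help. With no effects it gives 0.144, 0.179 and 0.244 for K = 3, 5 and 10.
- The cross-validated value stays within about 0.01 SD of the rule's true value and shows no gain over the best embedded strategy.

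**Step 3: the Monte Carlo comparison, if generated from this trial's fits.** Let q0, r, n0 and n1 be the fitted means for control, treatment responders, and non-responders without and with problem-solving. With 50% response, the values averaged over participants are:
- #1: mean of q0
- #2: mean of 0.5r + 0.5n0
- #3: mean of 0.5r + 0.5n1
- optimal: mean of max{q0, 0.5r + 0.5 max(n0, n1)}

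A mean of maxima is never below the maximum of the means, so the optimal strategy cannot lose. Over 1,500 trials per setting with K = 3, 5 and 10, its average lead was 0.073, 0.112 and 0.189 (no effects); 0.047, 0.076 and 0.140 (0.36 only); and 0.008, 0.019 and 0.055 (both).

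**Step 4: would the overall moderator test protect the comparison?** A simple version, with F tests at each stage and Bonferroni adjustment, rejected in about 5% of the no-effects trials. Among those trials the lead was larger: 0.138, 0.181 and 0.253 for K = 3, 5 and 10.

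**The case against.** The strongest reply is that this is labelled hypothesis-generating work, that the current SAP carries forward only the estimation of a strategy, and that any follow-on would be a new study. All of that is correct. It limits the consequence but does not remove the bias from the valuation the protocol describes.

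A reader might go further and infer that the comparison with #1 to #3 is bound to favour the personalised strategy. The documents do not support that. The per-participant sentence contains no comparison, and the Monte Carlo sentence gives no generating model. If the rule were re-estimated and valued on independent draws from a model not built on this trial's fits, the bias need not arise.

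Four further points deserve weight.
- With no true moderator the overall test would be non-significant about 95% of the time, so an apparent gain would usually appear beside a null moderator result. That tempers misreading, but nothing makes the valuation conditional on the test, and Step 4 shows that conditioning would not cure it.
- The number of tailoring variables is not stated, and variable selection is planned. The measures table in Protocol Section 8 lists 13 baseline instruments besides demographics and chart review, so 10 is possible. It is still an assumption, and several of those instruments measure Aim 2 outcomes.
- The largest of three estimates carries selection optimism too, averaging 0.076 to 0.080 SD with no effects. The excess over that benchmark is therefore the fair measure, not the raw apparent value.
- The bias is small where one embedded strategy is clearly best and few covariates enter.

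**Conclusion.** The concern holds for the per-participant valuation in Protocol Section 8.2, Aim 3: the strategy is scored in the sample that produced it, and no optimism correction is described. With 270 participants, no true moderator and 3 to 10 covariates, the apparent excess over the best embedded strategy is about 0.08 to 0.18 SD with no effects, 0.05 to 0.14 SD with a Stage 1 effect of 0.36, and 0.01 to 0.05 SD with an added 0.69 problem-solving effect. Cross-validation shows no gain in any of these settings. The sizes rest on the assumptions listed in the working.

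For the Monte Carlo comparison the conclusion is conditional: it is biased in the same way if generated from models fitted to this trial, and the protocol leaves that open.

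It would be wrong to infer that the trial's main findings are at risk. The primary analysis and the secondary comparison of #1 to #3 do not use the estimated strategy, so none of their conclusions changes.

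**What to change.** Amend Protocol Section 8.2, Aim 3, and add the valuation step to the SAP's Exploratory Analysis Plan, which now covers estimation only:

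1. Estimate the optimal strategy's value by cross-fitting. Derive the rule in all folds but one, apply it to the held-out fold, and score it with the inverse-probability-weighted mean the SAP already uses for the embedded strategies.
2. Report that value and its differences from #1, #2 and #3, with intervals that allow for the rule being estimated.
3. Label any in-sample per-participant gain as optimistic. It need not be dropped.
4. State the tailoring variables and the Monte Carlo generating model, and include a no-moderator scenario as a benchmark.

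The cost is a SAP paragraph, the matching protocol edit and analyst time; no new data are needed. The downside is a noisier and less flattering estimate of what personalisation offers.
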